**General Hospital, Tianjin Medical University**

**Zhongshan Hospital, Xiamen University,**

**Nanfang Hospital, Southern Medical University**

**The Affiliated Drum Tower of Nanjing University Medical School**

**SPONSOR:**

**Renji Hospital, Shanghai Jiao-Tong University School of Medicine**

## 1. Background

Colorectal cancer (CRC) is a leading cause of cancer deaths worldwide and in recent years its incidence is increasing rapidly in China, which constitutes a major public health burden [1]. Almost 90% of CRC cases develop from precursor adenomatous polyps, through a series of genetic changes known as adenoma-carcinoma sequence during at least 10 years [2]. Detection and removal of colorectal adenoma (CRA) could reduce CRC mortality risk by colonoscopy [3], but the recurrence rate is high [4]. Chemoprevention of adenoma and cancer remains its importance in both aspects of public health and cost effectiveness.

Our previous clinical trial has shown that supplementation of 1mg folic acid per day decreases significantly incidence of sporadic CRA in elder healthy people [5]. However, the role of folic acid in the prevention for CRA recurrence has kept controversial to date [6]. Favorable effects of several kinds of medicine on the secondary prevention of CRA have been reported in observational studies and randomized controlled trials (RCTs), including aspirin, vitamin D, etc. A latest meta-analysis summarized that regular intake of aspirin or COX-2 inhibitors seemed to be effective in preventing relapse of adenomas, but meanwhile a dose-related increase of gastrointestinal complications could be observed [7]. To evaluate the protective potential of vitamin D3 and/or calcium, a large-scale randomized trial conducted in 2259 participants with a recent history of CRA showed unfortunately no significant effect of any group [8]. Thus looking for suitable prophylactic drugs for CRA recurrence is urgent needed.

Berberine (BBR) hydrochloride, a natural isoquinoline alkaloid extracted from the Chinese herb *Coptis chinensis*, has been widely used in China to cure diarrhea and enteritis for centuries with minimal side effects [9], and accumulating evidences have showed its anticancer activity, but its molecular mechanism has not been quite clear. Our previous study presented that BBR could block the colorectal adenoma-carcinoma sequence in mice by changing microbiota structures [10]. In order to further evaluate its clinical potential for CRA recurrence, we have initiated this clinical trial of pharmacological intervention in persons after a recent polypectomy.

## **2. Objectives**

We initiate this placebo-controlled study to investigate the clinical potential of BBR hydrochloride in preventing recurrence and carcinogenesis after endoscopic removal of CRAs.

## **3. Design**

### **3.1 Overall design**

Double-blind, randomized, placebo-controlled trial

### **3.2 Randomization**

Computer-generated randomization is used to allocate participants into BBR hydrochloride group and placebo group in a 1:1 ratio. The person who generates the allocation sequence is an expert on biostatistics, who is not involved in this study. Investigators who enroll participants receive the serial numbers. Participant enrollment must be carried out according strictly to the serial numbers. Those who enroll participants and assign interventions are unaware of the details of grouping.

### **3.3 Blinding**

The participants, the investigators in charge of follow-up, the endoscopists and the pathologists are all blinded of which treatment the participant is receiving.

Unblinding will be advanced for an appropriate clinical management only in case of emergency.

## **4. Selection of Trial Population**

### **4.1 Inclusion criteria**

1. Individuals aged 18-75 years
2. Individuals who had at least one and no more than 6 histologically confirmed CRAs removed within 6 months before recruitment

3. Individuals who are able to swallow pills
4. Individuals who voluntarily sign the consent form after being fully informed and understanding the purpose and procedure of this study, characters of the disease, effect of medication, methods of related examinations, and potential risk/benefits of the study

#### **4.2 Exclusion criteria**

1. Individuals whose adenoma was not completely removed during previous colonoscopy
2. Individuals with a history of familial adenomatous polyposis (FAP) or hereditary non-polyposis colorectal cancer (HNPCC, Lynch syndrome)
3. Individuals who are taking regularly aspirin, nonsteroidal anti-inflammatory drugs (NSAIDs), cyclo-oxygenase 2 (COX2) inhibitors, calcium or vitamin D
4. Individuals with a history of subtotal/total gastrectomy or partial bowel resection
5. Individuals who are intolerant to another colonoscopy examination
6. Individuals who are hypersensitive or intolerant to the drugs
7. Individuals with severe heart, liver or kidney disease, or any cancer history
8. Individuals presenting severe constipation
9. Pregnant women, women during breast-feeding period, or women with expect pregnancy
10. Individuals with mental diseases who are not able to cooperate
11. Individuals who are involved in designing, planning or performing this trial

#### **4.3 Elimination criteria**

1. Individuals who do not meet the inclusion/exclusion criteria.
2. Serious violation of the study protocol which has impact on the drug efficacy.
3. Presence of lost data or data unable to get.

### **5. Numbers of Cases & Allocation**

According to the statistical sample size, we are planning to enroll 1000 cases in our study, 500 cases in each group.

## 6. Interventions

### 6.1 Medication

#### 6.1.1 Drug 1

- Ingredient: BBR hydrochloride
- Dosage form: Tablet

#### 6.1.2 Drug 2

- Ingredient: Placebo
- Dosage form: Tablet

All the study pills are provided by Shanghai SINE Pharmaceutical Co., Ltd.

### 6.2 Dose & usage

BBR hydrochloride 300mg Bid

Placebo 3# Bid

### 6.3 Duration

Until the last enrolled patient reached the 2-years follow-up.

### 6.4 Concomitant treatment

Conventional symptomatic treatment can be used in both group during the study period. When severe constipation occurs in participants after taking study pills, they are allowed to take one prokinetic drug within 2 weeks.

### 6.5 Participant timeline

The time schedule of enrollment, interventions and visits for participants is shown in a schematic diagram (Table 1) following the instructions in the SPIRIT 2013 (Standard Protocol Items: Recommendations for Interventional Trials) statement [11].

## 7. Observation Items

### 7.1 Demographic characteristic & medical history

Gender, age, height, weight, medical history, recent medication, smoking status, history of CRA, family history of CRC, clinical manifestations before enrollment, recent colonoscopy and biopsy, etc.

**Table1. Participant timeline**

|                                    | Study Period |        |                 |    |    |    |    |    |    |    |                           |
|------------------------------------|--------------|--------|-----------------|----|----|----|----|----|----|----|---------------------------|
|                                    | Allocati     | Run-in | Post-allocation |    |    |    |    |    |    |    | Closeout                  |
| Time points                        | 0            | -2wks  | M3              | M6 | M9 | 12 | 15 | 18 | 21 | 24 | M24-M36
Final visit    |
| Enrollment:                 |              |        |                 |    |    |    |    |    |    |    |                           |
| Eligibility screen                 | X            |        |                 |    |    |    |    |    |    |    |                           |
| Informed consent                   | X            |        |                 |    |    |    |    |    |    |    |                           |
| Interventions:              |              |        |                 |    |    |    |    |    |    |    |                           |
| BBR
hydrochloride or
placebo |              |        | ◆               |    |    |    |    |    |    | ◆  | Return
unused
pills |
| Assessments:                |              |        |                 |    |    |    |    |    |    |    |                           |
| Demographics                       | X            |        |                 |    |    |    |    |    |    |    |                           |
| Smoking status                     | X            |        |                 |    |    |    |    |    |    |    |                           |
| Height                             | X            |        |                 |    |    | X  |    |    |    | X  |                           |
| Weight                             | X            |        |                 |    |    | X  |    |    |    | X  |                           |
| Medical history                    | X            |        |                 |    |    |    |    |    |    |    |                           |
| Family history                     | X            |        |                 |    |    |    |    |    |    |    |                           |
| Manifestations                     | X            |        | ◆               |    |    |    |    |    |    | ◆  |                           |
| Laboratory tests                   | X            |        |                 |    |    | X  |    |    |    | X  |                           |
| Colonoscopy                        | X            |        |                 |    |    | X  |    |    |    | X  |                           |
| Histology                          | X            |        |                 |    |    | X  |    |    |    | X  |                           |
| Stool samples                      | X            |        |                 |    |    | X  |    |    |    | X  |                           |
| Drug distribution                  |              | ◆      |                 |    |    |    |    |    |    | ◆  |                           |
| Adverse event                      | X            |        | ◆               |    |    |    |    |    |    | ◆  |                           |
| Medication                         |              | ◆      |                 |    |    |    |    |    |    | ◆  |                           |

## 7.2 Observation index

### 7.2.1 Clinical manifestations

We record the clinical manifestations before recruitment and during the follow-up period, including symptoms (fatigue, lack of appetite, nausea, emesis, abdominal distension, diarrhea, change of stool character and abdominal pain) and signs (abdominal tenderness, mass, rebound tenderness, etc.).

### **7.2.2 *Laboratory examination***

We record the results of laboratory tests, including routine blood tests, hepatic and renal function at the baseline, and during the follow-up period.

### **7.2.3 *Colonoscopic examination***

Participants at each center are informed to undergo at least one or two follow-up colonoscopies until the last enrolled patient reached the 2-years follow-up, by a training endoscopist to investigate whether new adenoma will be taken place, using a standard colonoscope.

Bowel preparation includes 1000ml polyethylene glycol electrolyte solution administered the previous evening and 2000ml in the early morning before an intraday examination. If the colonoscopy does not reach the caecum, it cannot be included for further analysis and the patient will be required to undergo colonoscopy by another skilled endoscopist on next occasion. The mean colonoscopy withdrawal time are required to be 6 minutes or more.

According to a multiple-center study based of Chinese population [12], the peak of recurrence of adenomas is almost entirely concentrated in the first year, and the first three years follow-up after polypectomy is of critical importance in China. The similar opinions are recommended in *2011 Consensus on the Prevention of Colorectal Tumors in China* [13].

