## **11. Endpoints**

The primary endpoint is the recurrence of CRA at any follow-up colonoscopy in both groups during the whole trial. The number, size and location of all adenomas are assessed.

The secondary outcomes are the incidence rates of all polypoid lesions (hyperplastic polyps, inflammatory polyps, serrated polyps, etc.), as well as advanced adenoma or CRC at any follow-up colonoscopy in both groups.

All retrieved polypoid lesions should be sent to local pathology laboratory for histologic evaluation. Two experienced pathologists at each center, who are unaware of the treatment assignments, must review the slides for all removed colorectal lesions. Disagreements in the histologic diagnosis are resolved by re-examination by these two pathologists until agreement is reached. We classify the location of a lesion as right

sided (caecum, ascending colon, hepatic flexure, and transverse colon) or left sided (splenic flexure, descending colon, sigmoid colon, and rectum), and define advanced CRA (A-CRA) as an adenoma with a diameter of 10 mm or more, a villous adenoma ( $\geq 25\%$  villous) or an adenoma with high-grade dysplasia.

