## 13.2 Statistical analysis

### 13.2.1 Balance analysis

Full Analysis Set (FAS) is used in the balance analysis. This analysis set includes all the subjects to the principle of intention to treat (ITT). The subjects must have received at least one follow-up colonoscopy.

A balance analysis is performed for baseline data to evaluate the comparability of the two groups. The baseline data include the number of patients enrolled, the number of clinically evaluable patients, age, weight, symptoms, signs and laboratory tests. In the balance analysis, quantitative variables are described using the mean, standard deviation (SD), normal distribution W test and  $P$  value, etc. The t test or the Wilcoxon rank sum test (if abnormal distribution) is used for comparison the difference between the test drug group and the control group in the statistical analysis. Categorical variables are described using cases and percentages. The chi-square ( $\chi^2$ ) test, the Mantel-Haenszel  $\chi^2$  test or the Fisher's exact test is used for analyzing categorical data.

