### 13.2.2 Efficacy analysis

The trial results are evaluated by FAS and Per Protocol Set (PPS). FAS is mainly used to compare the treatment effect for the primary endpoint, and regarding the statistical results from PPS as supplementary analysis. If the subjects have not completed all the treatment, the last exam result will be treated as last observation carried forward (LOCF). Risk ratios (RR) and 95% confidence intervals (CI) are used as the efficacy indicator, comparing by Mantel-Haenszel  $\chi^2$  test methods between the two groups.

Unconditional logistic regression is conducted to compute the odds ratio to estimate the relation between BBR intervention and recurrence of A-CRA and non A-CRA (NA-CRA). Kaplan-Meier method is conducted to estimate progression-free survival of no recurrence of adenoma with log-rank test to compare the survival curve between BBR and placebo group. Survival Curve is used to illustrate time to recurrence of adenoma and RRs are illustrated by Forest plots. We perform predefined subgroup analyses of the primary outcomes to assess BBR effect in terms of age, gender, smoking status, BMI, family history of CRC, number of adenoma and history of CRA.

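### A colonoscopy that misses the caecum is barred from analysis even if it found a confirmed adenoma, so a proven recurrence can be scored as none or dated late; the effect is small

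*Combined protocol and SAP*

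**What the plan says.** Section 7.2.3 sets the completeness rule: "If the colonoscopy does not reach the caecum, it cannot be included for further analysis". The same sentence continues that "the patient will be required to undergo colonoscopy by another skilled endoscopist on next occasion". No time limit is given for that repeat. Participants are "informed to undergo at least one or two follow-up colonoscopies", and Table 1 places these exams at months 12 and 24.

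Section 11 sets the endpoint: "The primary endpoint is the recurrence of CRA at any follow-up colonoscopy in both groups during the whole trial". The secondary outcomes use the same scope, "as well as advanced adenoma or CRC at any follow-up colonoscopy in both groups". Neither carries a condition that the caecum was reached. Section 11 also says that two pathologists "must review the slides for all removed colorectal lesions", again without that condition.

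Section 13.2.1 defines the full analysis set (FAS): "The subjects must have received at least one follow-up colonoscopy". It does not say whether that exam must be complete. Section 13.2.2 carries the last exam result forward for participants who did not complete treatment, and uses Kaplan-Meier and log-rank for time to recurrence. It does not say whether an incomplete exam supplies a result or a date.

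**The concern.** The two possible results of an incomplete exam do not carry the same information. A negative one says nothing about the segment that was not seen, so leaving it out is right. A positive one with histological confirmation is already the primary event, whatever lies beyond the point reached. Section 7.2.3 treats them alike, and no section says how the second kind is counted or dated.

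Followed as written, the rule can go wrong in three ways:

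- **Lesion removed at the incomplete exam.** The repeat cannot find it. If no other adenoma appears, the participant is scored as recurrence-free, even though the repeat was done as required.
- **Lesion left in place and found later.** The event is kept but dated late. With exams at months 12 and 24 the delay could reach 12 months; an earlier repeat would shorten it.
- **Month 12 complete and negative, month 24 incomplete and positive, repeat not done.** The month-12 negative is then the only usable result. This does not depend on removal, but it does need a departure from the repeat requirement.

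At stake are a few misclassified primary events, some late Kaplan-Meier event times, and the possibility that analysts settle the question differently once data are visible.

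**Working it through.** **Inputs from the documents.** Recurrence 30% on placebo and 21% on berberine (BBR), 80% power, 20% dropout, 918 individuals (13.1); two-sided 0.05 (13.2.4); 1000 planned (section 5).

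**Assumptions, because the documents give no figures.** i = share of exams that are incomplete, 5% (range 2–10%). s = share of recurrences seen in the segment reached, 50–70%. r = share of incomplete exams that are repeated. w = share of recurrences present at month 12, 50–80%.

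**1. The plan's own figure.** With pooled null variance:

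n = [1.960·√(2·0.255·0.745) + 0.842·√(0.30·0.70 + 0.21·0.79)]² / 0.09² = 367 per arm.

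367/0.8 rounds up to 459 per arm, or 918 in total. The stated size reproduces. Power is 80.0% at 367 per arm and 83.3% at 400 per arm (1000 less 20%).

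**2. Ceiling under the current rule.** Lesion removed, every repeat done, nothing else found. A share i·s of true recurrences is lost, so the observed rate is p(1 − i·s).

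- Placebo: 0.30 × (1 − 0.025) = 29.25% to 0.30 × (1 − 0.035) = 28.95%. Loss 0.75–1.05 points, or 2.8–3.9 events per 367.
- BBR: 0.21 × (1 − 0.025) = 20.48% to 0.21 × (1 − 0.035) = 20.27%. Loss 0.53–0.74 points, or 1.9–2.7 events per 367.
- Risk ratio (RR): the factor (1 − i·s) cancels, so it stays 0.70.
- Power: 78.7–78.1% at 367 per arm (loss 1.3–1.9 points); 82.0–81.5% at 400.
- For i from 2% to 10%, the placebo loss is 0.30 × 0.02 × 0.5 = 0.3 points to 0.30 × 0.10 × 0.7 = 2.1 points.

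**3. Milder cases, i = 5%.**

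- Two exams, lesion removed, repeats done, 30% chance of another adenoma at month 24: loss = p·i·s·[w(1 − 0.3(1 − i·s)) + (1 − w)] = 0.57–0.90 points. Power is 78.4–79.0% at 367.
- Lesion left in place, repeats done: no event lost, later date only.
- One exam, no repeat: the participant leaves the analysis whatever was found, and the rate still reads 30.0%.

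**4. Check of the remedy.** A positive incomplete exam counts, and evaluability requires at least one complete exam.

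- One exam: [p(1 − i) + i·r·p] / [(1 − i) + i·r] = p. It reads 30.0% and 21.0% at every repeat rate.
- Two exams, no repeats, lesion removed, no further adenoma. Current rule: p[1 + w·i(1 − s)]/(1 + i) = 28.8–29.1%. Remedy: p[w + (1 − w)(1 + i·s)/(1 + i)] = 29.6–29.9%. RR is 0.70 under both.

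**5. Unequal incomplete rates (hypothetical).** No treatment effect, 10% incomplete in one arm and 5% in the other, lesion removed, repeats done. The current rule reads 27.9–28.5% against 28.95–29.25%, RR 0.96–0.97.

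**The case against.** The strongest reply is that the sections can be read together: section 7.2.3 says which exams may enter analysis, and section 11 then means any admitted exam. That reading is available, so this is not a flat contradiction. But no section states it, and under it a confirmed adenoma removed at an incomplete exam is still scored as no recurrence.

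A second reply is that the required repeat is the remedy. It is, for lesions that were missed and for lesions left in place. It cannot recover a lesion already taken out. It is fair to add that section 11 speaks of removed lesions in general and nowhere says that lesions are removed at an incomplete exam.

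A third reply has real force: a completeness rule that ignores the result keeps evaluability independent of outcome. If a positive incomplete exam alone made a participant evaluable while a negative one did not, then with one exam and no repeats the 30% rate would read (0.285 + 0.0075)/(0.95 + 0.0075) = 30.5% to (0.285 + 0.0105)/(0.95 + 0.0105) = 30.8%. The remedy should therefore leave evaluability tied to a complete exam.

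A reader might also infer that the rule biases the treatment comparison. The documents do not support that. Bias in the RR needs incomplete rates that differ between arms. No rates are given, and endoscopists are blinded (3.3). Section 6.4 foresees constipation on study pills but gives no frequency by arm.

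**Conclusion.** The point holds, and it is minor. The rule is right for negative incomplete exams and wrong for positive ones: it can turn a proven primary event into a non-event, or move its date. On the central assumptions the ceiling is 0.75–1.05 points of the placebo rate and 1.3–1.9 points of power at 367 per arm. At 400 per arm power stays above 80%. With equal incomplete rates the RR is unchanged.

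Every rate behind these figures is assumed, and the ceiling also needs removal at the incomplete exam, which is implied only. Nothing here shows a biased RR, an error in the 918, or a reason to drop the completeness rule for negative exams. It is worth settling because it decides whether a confirmed event counts, and section 13 allows the plan to be modified before data lock.

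**What to change.** The change concerns counting only; the repeat requirement in section 7.2.3 stays as written. State in 7.2.3, 11 and 13.2:

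- A histologically confirmed adenoma (for the secondary endpoints, any qualifying lesion) found at any follow-up colonoscopy, complete or not, counts as an event and is dated to that exam.
- An incomplete exam without such a lesion is not evidence of no recurrence.
- For the primary analysis, every participant needs at least one complete follow-up colonoscopy, the repeat included, whatever was found.
- One sensitivity analysis adds participants whose only exam was incomplete and positive, counted as events.

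A table by arm of incomplete exams, and of those not repeated, is optional; it would show whether the rates differ.

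The cost is a few sentences and one sensitivity analysis, with no added procedure. The downside is that the few participants whose only exam was incomplete and positive stay out of the primary analysis. That is the price of keeping evaluability independent of outcome.
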